8. STATISTICAL CONSIDERATIONS

8.1 Primary Endpoint

8.1.1 Study Design/Study Endpoints

The study is a prospective single-arm phase II trial of Image Guided Hypofractionated Radiation Treatment in the definitive treatment of locally advanced cervical cancer. The study will determine whether Image Guided Hypofractionated Radiation Treatment boost is efficacious in women with locally advanced cervical cancer without increased risk of acute GI or GU toxicity. Study endpoints include local control rate, and toxicity assessed by CTCAEv4,

For the safety lead-in not more than 1 of 6 patients should have more than Grade 2 toxicity over 90 days after commencement of Image Guided Hypofractionated Radiation Treatment boost

8.2 Secondary Endpoints

The secondary objectives are to:

- Determine the late grade ≥ 3 GI and GU toxicity as assessed by CTCAE v4 at 91-365 days from the start of protocol treatment. *This will be summarized using a proportion and a 95% confidence interval.*
- Measure Cervix cancer specific patient reported QOL at 6 time points using FACT-CX validated measurement tools with our VTOC system

8.3 Sample Size

8.3.1 Overview

Six patients will be used for a safety lead-in stage in this phase II clinical trial. In Standard Phase 1 3+3 clinical trials, there is 0 or 1 DLT out of 6 patients at the MTD, which will be used for a subsequent phase II clinical trials. [36] Prior studies have shown the rate of \geq grade 3 GI toxicity to be 7-14% and 2-5% for \geq grade 3 GU toxicity. The treatment will not be considered to be feasible if the rate of acute GI/GU toxicity is $>30\%$. In this phase II clinical trial, six patients will be used in a safety lead-in stage. If there is 0 or 1 DLT out of 6 patients at the safety lead-in stage, we will proceed to a phase II clinical trial. Otherwise, we will stop the trial, and will not proceed to a phase II trial with a given dose.

The primary goal of this study is to assess the 2 year pelvic local control (excluding nodes) from cervix cancer. Historical data shows that the 2 yr-pelvic local control rate is approximately 65%. [4, 5, 9] We expect that this will be increased to 85% with the treatment of cervix Image Guided Hypofractionated Radiation Treatment boost based on best results with Intracavitary/interstitial data [13]. We assume that the loco regional recurrence-free survival follows an exponential distribution. Accrual to the study is assumed to be uniformly distributed over time with no loss to follow-up. Twenty-one patients will achieve 80% power in detecting the difference between the null hypothesis of 2-year recurrence-free survival rate of 65% and the alternative hypothesis of 2-year recurrence-free survival rate of 85% at a two-sided 0.1 significance level assuming a 2-year accrual period and 2-year follow-up period. It is expected that 21 patients will be recruited in 2 years with an expected accrual rate of 10-11 patients per year.

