1. BACKGROUND AND RATIONALE

1.1 Disease Background

Locally Advanced Cervical Cancer (LACC)

There will be an estimated 12,300 new cases of cervical cancer diagnosed in the United States in 2013, with one third that number dying from the cancer [1]. While the incidence of cervical cancer in the United States has been gradually declining as a result of widespread screening, outcomes still remain poor for many with cervical cancer. In addition there has been a negligible survival improvement over the past decade. [2] Even with the increased screening in the U.S., 48% of patients still present at an advanced stage [2]. Globally cervical cancer is widespread (no. 3 cancer in women) and lethal (with a mortality incidence ratio of 52%) [3]. Several prospective randomized trials compared concurrent chemotherapy and radiation to radiation alone for advanced cervical cancer and showed substantial improvement in local control and overall survival in the late nineties [4, 5]. As a result, the National Cancer Institute issued a treatment alert in 1999 establishing chemoradiation as the standard of care for advanced cervical cancer. Radiotherapy for cervical cancer currently consists of radiation in the form of external beam delivered over 5-6 weeks of daily therapy followed by or interdigitated with intracavitary or less frequently, interstitial brachytherapy. These procedures remain invasive and require use of supportive medications ranging from general anesthesia in the operating room to a combination of sedatives and narcotics for insertion of the brachytherapy devices. Furthermore, intracavitary brachytherapy delivers dose to a limited volume of tissue around the cervix and may be inadequate for delivering dose to tumors that extend to the pelvic sidewall. As a result, even with the use of chemoradiation, approximately 30% of patients with locally advanced disease will have a locoregional recurrence [5]. These results of best local control for Stage III-IVA cervix cancer of 70% applies to carefully chosen patients in clinical trials. Patients with bulky advanced cervical cancers like the vast majority of patients we see at Parkland (PMH) and UTSW have an inferior local control which is hampered by poor performance status of these patients. In a recent review of patients from 2003-2011 at PMH, the actuarial overall survival for all II-IVa pts was only 34% at 5 years [6]. A significant group of patients had locoregional failure or persistence, presumably due to bulky tumor volume exceeding the limitations of available radiation and chemotherapeutic modalities. Additionally, patients often present with multiple untreated co-morbidities which makes them often unable to undergo standard chemoradiation and brachytherapy often compromising the delivery of adequate radiation dose and hence the tumor local control. Furthermore, current treatments are often unpalatable for many patients because they are either too invasive, inconvenient or inadequate.

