
The implementation of Intracavitary brachytherapy (which is the most commonly applied form of Brachytherapy in the US) [7] in bulky tumors (esp. Stage IIIB tumors which extend to the pelvic side-wall), results in inadequate dosage to tumor especially at side-wall of pelvis. This occurs because of the rapid falloff of radiation dose from intracavitary brachytherapy sources which may explain the relatively high rate of local failure in bulky stage III cervical cancers.

More advanced methods of delivery are available, like Image Based high dose rate Brachytherapy with the Europeans being the innovators in this area. Under the aegis of the GEC-ESTRO group many new frameworks for HDR Cervix brachytherapy have been introduced with emphasis on volumetric assessment of dose to cervix CTV recommended to be based on MR imaging [8]. The most updated French Multicentric experience of over 600 patients with cervical cancer comparing 2D with 3D image based intracavitary brachytherapy

showed that in the advanced cervical cancer patients (mostly stage II; as IIIB were only 25% of group) local recurrence was still 25%. They did not break up recurrence by stage.[9]

For the bulkier tumors, in order to improve tumor control, interstitial brachytherapy is recommended by some. These are more invasive procedures and involve transperineal Interstitial needle placement into cervix tumor with General anesthesia, hospital inpatient stay, extensive support and involvement of considerable resources and provider-hours. Even with these invasive procedures, the best results provide 60-65% local control at 2-3 years for all stages [10, 11]. This is an important problem, since locally advanced cervical cancer continues to recur despite current treatments and more effective, less toxic and more convenient treatments are necessary.

The Vienna group has pioneered a combined Intracavitary- Interstitial technique which requires Intra-operative MRI suite which is impractical in the US setting and particularly in the county hospital setting which we work in.[12]

Their best results with IIIB disease are using 3D image based hybrid version of Intracavitary/interstitial brachytherapy using a customized ring applicator with needles achieved a local control of 86% for IIIB cancer .[13]This process is very resource intensive and requires interstitial MR guided-Brachytherapy expertise which may not be available in most US centers.

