2. STUDY OBJECTIVES

2.1 Primary Objective

The primary objective is to improve primary tumor local control of eligible LACC using Image Guided Hypofractionated Radiation Treatment as the mechanism for delivering boost therapy to 85% at 2 years post treatment.

A phase I safety lead-in will be performed as described in section 8.

For the safety lead-in phase, acute grade ≥ 3 gastrointestinal (GI) toxicity (perforation, obstruction, bleeding, ulceration, necrosis, proctitis and diarrhea requiring elective or urgent hospitalization) and grade ≥ 3 genitourinary (GU) toxicity (cystitis, hematuria and incontinence requiring elective or urgent hospitalization) within 90 days from the commencement of Image

Guided Hypofractionated Radiation Treatment boost will be assessed. Toxicity will be graded according to the Common Terminology Criteria for Adverse Events (CTCAE) version 4.

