7.1.6 Progression-Free Survival

Progression-free survival (PFS) is defined as the duration of time from start of treatment to time of progression.

This will be further differentiated as Local tumor (cervix-which is primary endpoint) , Regional(pelvic nodal) and distant (Paraortic and visceral organ)metastases.

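### The 65% null is not shown to be on the nodes-excluded definition of the primary endpoint; any nodal-only failures it counts would tilt the only efficacy test towards the boost

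*Combined protocol and SAP*

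**What the plan says.** Three sections make the endpoint cervix-only.

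- Section 2.1: "The primary objective is to improve primary tumor local control of eligible LACC".
- Section 7.1.6 names the component "Local tumor (cervix-which is primary endpoint" and keeps a separate category, "Regional(pelvic nodal".
- Section 8.3.1: "The primary goal of this study is to assess the 2 year pelvic local control (excluding nodes) from cervix cancer".

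The benchmark is in the same paragraph of 8.3.1: "Historical data shows that the 2 yr-pelvic local control rate is approximately 65%. [4, 5, 9". What the protocol reports from those three references differs.

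- Reference 5 (section 1.1): "approximately 30% of patients with locally advanced disease will have a locoregional recurrence [5". The next sentence but one calls the result local control: "These results of best local control for Stage III-IVA cervix cancer of 70% applies to carefully chosen patients in clinical trials".
- Reference 9 (section 1.1): local recurrence of 25%, with no time point.
- Reference 4: no control figure and no failure definition.

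The 85% alternative cites reference 13, which section 1.1 reports as local control: "achieved a local control of 86% for IIIB cancer".

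The power model in 8.3.1 is for locoregional recurrence-free survival. The one-sample log-rank test in 8.5.1 is for local recurrence-free survival, against 65%.

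**The concern.** The trial is single-arm, and its only efficacy test compares the observed control with a fixed 65%. That comparison is fair only if both sides count the same events. Leaving nodal-only failures out of the trial's count, while some remain in the benchmark, raises observed control relative to the null with no treatment effect. The error can go only one way, in favour of the boost. The 85% alternative is already reported as local control, so part of the planned 20-point gain could come from the change of definition.

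**Working it through.** **Inputs (8.3.1).** Null 65% and alternative 85% at 2 years, exponential times, uniform accrual over 2 years plus 2 years of follow-up, no loss, two-sided 0.10, 21 patients. Sections 8.3.2 and 8.4.1 expect 3 years of accrual, so ranges below span 2- and 3-year accrual where both were run.

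**Reproducing the plan's figure.** Hazards are λ0 = −ln(0.65)/2 = 0.2154 and λ1 = −ln(0.85)/2 = 0.0813 per year. Under the alternative with 2-year accrual, the event probability is d1 = 0.2155. The expected count per patient under the null is e = d1·λ0/λ1 = 0.5712. For the one-sample log-rank test,

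N = [(1.645·√e + 0.8416·√d1)/(e − d1)]² = [(1.2432 + 0.3907)/0.3557]² = 21.1.

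The 21 patients reproduce. Simulated power (200,000 trials, Z = (O − E)/√E, benefit if Z < −1.645) is about 77% with 2-year accrual. The chance of declaring benefit when true control is 65% is about 3.7%. It is below the nominal 5% per side because the test is conservative in that tail at this size.

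**Moving the null to the nodes-excluded definition.** Let s be the share of locoregional failures that are nodal only. The documents do not give s, so 10%, 20% and 30% are assumptions. How much of the 65% is locoregional is also not given, so two cases are shown.

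- One third of the null locoregional (three references weighted equally, illustrative): matched rate = 1 − 0.35·(1 − s/3).
- All of it locoregional (upper bound): matched rate = 1 − 0.35·(1 − s).

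| s | One third: matched rate | False benefit | All: matched rate | False benefit |
|---|---|---|---|---|
| 10% | 66.2% | about 5% | 68.5% | 8–9% |
| 20% | 67.3% | 6–7% | 72.0% | 16–17% |
| 30% | 68.5% | 8–9% | 75.5% | 28–31% |

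False benefit is the chance that a boost with exactly the matched rate is declared better than 65%. Applying s to the hazard instead of the 2-year risk, in the upper-bound case, gives matched rates of 67.9%, 70.9% and 74.0%, and false benefit of about 7%, 13% and 22% with 2-year accrual. The direction is the same and the size somewhat smaller.

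**Effect of a higher null on power.** With 85% kept as the alternative, 21 patients give about 55–61% power against a 70% null and 31–36% against a 75% null. The same formula with 2-year accrual gives about 35 and 72 patients for 80% power. The 70% and 75% are the complements of the recurrence figures in section 1.1 for references 5 and 9. They are illustrations, not proposed nulls.

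**The case against.** A reader might infer that 65% is a locoregional rate, that it must be too low, and that an ineffective boost would look like an improvement. The documents do not support that.

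- Section 8.3.1 itself labels the 65% pelvic local control. Of its three references, only reference 5 is reported as locoregional; reference 9 is reported as local and reference 4 is undefined.
- The 65% is not reference 5's figure. A 30% recurrence is 70% control, and reference 9's 25% is 75%. The null is already below both.
- Section 1.1 says the site's own patients have inferior local control. It also quotes 60–65% local control at 2–3 years for interstitial brachytherapy, and section 3.1 admits patients who need that treatment. Both could justify a lower local-only null.
- Even in the worst case shown, about 69% of trials of an ineffective boost would not declare benefit.

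All of this stands against the stronger reading. It does not remove the point. Section 8.3.1 cites neither the site's results nor the interstitial series for the null, and it describes no adjustment. An offset that is not written down cannot be checked. The conflict between locoregional in the power model and local in the test remains whatever the 65% represents.

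**Conclusion.** The point holds in limited form. It is certain that the plan uses more than one event definition against a single 65%, that one of the null's three references is reported as locoregional, and that nothing shows the null to be on the nodes-excluded definition. The direction is also clear: any nodal-only failures in the null favour the boost.

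The size is not known. The upper bound of about 8–31% requires every one of the 35 points of failure to be on a locoregional count, which the documents do not show. The one-third case of about 5–9% rests on equal weighting of the references, which is also an assumption. Both rest on assumed nodal-only shares of 10–30%. If the site's lower control rate or the interstitial figures were the real basis for 65%, the bias could be smaller or absent. This should be corrected, but it does not show that the planned test would usually mislead.

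**What to change.** Use the nodes-excluded local-failure definition throughout 8.3.1 and 8.5.1, and replace locoregional recurrence-free survival in the power model. Derive the null from local-only rates in a comparable population, and state the source and any downward adjustment for the site's patients. Keep the alternative on the same definition and restate the power for 21 patients. Control including pelvic nodes can be reported as a descriptive Kaplan-Meier estimate, since 7.1.6 already separates regional failure.

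Counting nodal failures in the test itself is not a good alternative. It would replace the objective in 2.1, and it would create the reverse mismatch with references 9 and 13, which are reported as local. It would also lean on nodal status at 2 years, when 6.3.1 requires axial imaging only once within fourteen months. The same limit should be stated beside the descriptive estimate.

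The cost is wording in two sections and a return to the cited sources for node-excluding rates. The stated power may become less favourable.

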6.3 Follow-up Procedures

Patients will be followed for 5 years after completion of treatment or until death, whichever occurs first. Patients removed from treatment for unacceptable adverse events will be followed until resolution or stabilization of the adverse event. Patients will be seen at clinic at 1 month, 3 months, 6 months, 12 month, 18 month, 24 month, then annual for 3 more years post-therapy for evaluation of disease progression as well as radiation toxicities.

- For the purposes of this protocol completion of therapy will be considered the day on which the fourth and final fraction of Image Guided Hypofractionated Radiation Treatment is delivered
- Any visit between one month and four month after the completion of therapy will be considered the three months visit
- Any visit between five months and eight months after completion of therapy will be considered the sixth month follow up
- Any visit between ten months and fourteen months after the completion of therapy will be considered the one year follow up
- Follow ups beyond one year can be scheduled \pm 2 month for each time point.

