6.5 Removal of Subjects from Study

Patients can be taken off the study treatment and/or study at any time at their own request, or they may be withdrawn at the discretion of the investigator for safety, behavioral or administrative reasons. The reason(s) for discontinuation will be documented and may include:

- 6.5.1 Patient voluntarily withdraws from treatment.
- 6.5.2 Patient withdraws consent)
- 6.5.3 Patient is unable to comply with protocol requirements
- 6.5.4 Patient demonstrates disease progression (unless continued treatment with study drug is deemed appropriate at the discretion of the investigator).
- 6.5.5 Patient experiences toxicity that makes continuation in the protocol unsafe.
- 6.5.6 Treating physician judges continuation on the study would not be in the patient's best interest.
- 6.5.7 Patient becomes pregnant during active treatment (pregnancy to be reported along same timelines as a serious adverse event).
- 6.5.8 Lost to follow-up. *Example language: If a research subject cannot be located to document survival after a period of 2 years, the subject may be considered "lost to follow-up." All attempts to contact the subject during the two years must be documented and approved by the Data Monitoring Committee.*

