8.3.2 Sample Size Derivation

Sample size was determined by estimating the number of potential patients likely to be (approximately 50% of referred patients meeting the eligibility criteria) to the UTSW Department of Radiation Oncology over a three year period. We estimate that approximately 50-60 patients meeting entry criteria will present to our facility over the accrual period of 3 years. Of these patients, slightly more than 50%, or 25-30 patients, will consent to be evaluated for the protocol. Of these patients, approximately 80% will meet the Image Guided Hypofractionated Radiation Treatment constraints for total of 20-24 patients enrolled over 3 years. Twenty one patients are required for a 80% power of detecting the improved pelvic local control for 2 year follow-up. The sample size was estimated using the SWOG one-sample survival calculator: http://www.swogstat.org/stat/public/one_survival.htm

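### The 80% power for 21 patients holds only with complete follow-up; with deaths at the protocol's own survival rate it is about 70-76% under the stated 2+2-year schedule

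*Combined protocol and SAP*

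**What the plan says.** Section 8.3.1 tests a 2-year rate of 65% against 85% with 21 patients, exponential failure times and 80% power, "at a two-sided 0.1 significance level assuming a 2-year accrual period and 2-year follow-up period". It adds: "Accrual to the study is assumed to be uniformly distributed over time with no loss to follow-up". Section 8.3.2 repeats the claim: "Twenty one patients are required for a 80% power of detecting the improved pelvic local control for 2 year follow-up". The planned enrolment in the study summary is also 21, so nothing is added for attrition. Section 8.5.1 names a one-sample log-rank test against 65%.

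Other sections bear on the follow-up assumption:

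- Section 1.1, on the study hospital's 2003-2011 series: "the actuarial overall survival for all II-IVa pts was only 34% at 5 years". It adds, without a figure, that a sizeable group had locoregional failure or persistent disease.
- Section 3.1 admits FIGO IB2 to IVB, Zubrod 0-3, and women whose other illnesses rule out brachytherapy.
- Section 6.3: "Patients will be followed for 5 years after completion of treatment or until death, whichever occurs first".
- Section 6.5 allows withdrawal and has a loss rule for when "If a research subject cannot be located to document survival after a period of 2 years", marked as example language and giving no rate.
- Sections 7.1.6, 8.3.1 and 8.5.1 call the endpoint progression-free survival, local control, recurrence-free survival and time to local failure. None says whether death without local failure is an event or is censored.

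**The concern.** The one-sample log-rank test compares observed local failures with the number expected under the 65% null, and that expected number is proportional to person-time. The sizing gives every woman 2 to 4 years of observation unless she fails locally. A woman who dies or is lost first contributes less, and the protocol's own survival figure says that this will be common.

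Fewer than five local failures are expected if the treatment works as hoped, so modest losses of person-time matter. If the trial does not reach significance, readers will judge that result against an 80% chance of detection that the stated schedule does not deliver.

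**Working it through.** **Inputs.** From 8.3.1: N = 21; 2-year rates 0.65 and 0.85; two-sided 0.10 (z = 1.645); entry uniform over 2 years plus 2 years, so planned observation is uniform on 2 to 4 years. From 1.1: 34% survival at 5 years. Constant hazards give:

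- null: -ln(0.65)/2 = 0.2154 per year
- alternative: -ln(0.85)/2 = 0.0813 per year
- death: -ln(0.34)/5 = 0.2158 per year, so exp(-2 x 0.2158) = 65% alive at 2 years

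**Formula.** Let c be the censoring hazard and h = 0.0813 + c. Mean observed time per patient under the alternative is m, the average of (1 - exp(-ha))/h over a uniform on 2 to 4 years. Observed failures are O = 21 x 0.0813 x m, and null-expected failures are E = 21 x 0.2154 x m. Power = Phi{[(E - O) - 1.645 sqrt(E)] / sqrt(O)}.

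**The plan's own figure.** With c = 0, m = 2.65 years, O = 4.53 and E = 11.99. The numerator is 7.47 - 5.70 = 1.77; dividing by sqrt(4.53) = 2.13 gives 0.83, and Phi(0.83) = 79.8%. The stated 80% reproduces. Simulation of the same test gives 77%.

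**With deaths.** The share of the death hazard made up of deaths without prior local failure is not in the documents, so it is an assumption and is varied. The 62% row subtracts the local-failure hazard under the alternative from the death hazard: 0.2158 - 0.0813 = 0.1345, and 0.1345/0.2158 = 62%.

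| Share of deaths censored | c per year | m (years) | O | E | Formula power | Simulated |
|---|---|---|---|---|---|---|
| 0 | 0 | 2.65 | 4.5 | 12.0 | 79.8% | 77% |
| 25% | 0.054 | 2.45 | 4.2 | 11.1 | 75.7% | 74% |
| 50% | 0.108 | 2.27 | 3.9 | 10.3 | 71.6% | 71% |
| 62% | 0.1345 | 2.19 | 3.7 | 9.9 | 69.6% | 69% |
| 100% | 0.2158 | 1.97 | 3.4 | 8.9 | 63.5% | 64% |

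At 50%, 18% of women are censored before 2 years; at 100%, 33% are. Dropout alone, with no deaths, at an assumed 5% or 10% per year gives 76% or 72% by formula (74% or 71% simulated).

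**Other test forms.** The 62% and 100% cases were also run for an exponential estimate on the cube-root scale: it starts at 81.9% and falls to 75.8% and 72.2%. A log-rank form with variance (O + E)/2 starts at 84.3% and falls to 79.1% at 50% and 74.2% at 100%. The levels differ, but the loss of up to about 10 points remains.

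**Longer observation, same 21 patients, 50% share.**

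| Schedule | Simulated | Formula |
|---|---|---|
| 3-year accrual (as in 8.3.2 and 8.4.1) + 2 years | 75% | 77% |
| 2-year accrual + 3 years | 79% | 82% |
| 3-year accrual + 3 years | 81% | 86% |
| 5 years for every patient | 84% | 88% |

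**The case against.** The strongest reply is that the plan discloses its assumption and its arithmetic is right. That stands: the stated inputs give 79.8%, so this is an untenable input and not a miscalculation.

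A reader might go further and infer that power falls to 64-72%. The documents do not support that as a headline. The 64% end treats every death as free of local failure, yet section 1.1 says that many of those patients failed locally. Such patients are already events, and counting their deaths as censoring counts them twice. At the other extreme, subtracting the whole null local-failure hazard leaves 0.2158 - 0.2154, about 0.0004 per year, and no loss of power. That needs essentially no death before local failure, which is implausible when stage IVB and Zubrod 3 are eligible. The 34% covers stages II-IVa, while eligibility runs from IB2 to IVB, so the death rate in this trial could lie on either side of it.

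A reader might also infer that 21 patients cannot supply the needed exposure. That is too strong. Section 6.3 follows each patient for 5 years, and section 8.5 sets no time for the primary test, so a later analysis recovers much of the exposure. Nor can the loss rule in 6.5 support a figure, since it gives no rate.

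Finally, treating deaths as censored is itself an assumption. Counting them as events would not rescue the 80%: with about 65% alive at 2 years on the historical rate, an 85% recurrence-free rate would also require far fewer deaths.

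**Conclusion.** The concern holds in a limited form. The 80% in 8.3.1 and 8.3.2 requires complete follow-up over 2+2 years, and the protocol's own survival figure makes that untenable. Power under that schedule is about 70-76% by formula (69-74% simulated), with 64% as a lower bound.

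This rests on a constant death hazard taken from the 34% five-year figure, on death without local failure being independent censoring, and on such deaths making up an assumed 25% to about 60% of all deaths. About 3 points of the gap between 80% and the simulated values come from the formula's approximation (77% simulated with no loss), not from attrition. The shortfall belongs to the stated schedule and does not show that 21 patients are too few for any analysis time.

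**What to change.** 1. In 8.3.1, replace the no-loss assumption with a stated censoring hazard for death without local failure, derived from the 34% survival figure, plus one for dropout.
2. In 8.3.1 and 8.3.2, restate the power as a conditional range: 80% only with complete follow-up, and about 70-76% if 25% to about 60% of deaths occur without local failure. Any dropout allowance lowers this further.
3. In 8.5.1, state that death without local failure is censored in the one-sample log-rank test, and use one endpoint name throughout.
4. Fix the time of the primary analysis. With at least 3 years of follow-up per patient, power at half of deaths is about 79-82% (2-year accrual) or 81-86% (3-year accrual), simulated to formula, with the same 21 patients and within the follow-up already planned.

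The cost is a few sentences and one rerun of the calculation. The sponsor accepts either a less favourable stated power or a primary analysis about a year later.
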